Physical exam ^f		X		X			X	X	
Pulmonary function testing		X		X			X		
██████████		X		X			X		
Right heart catheterization									
V/Q scan ⁱ									
Pregnancy test for WOCBP ^k		X		X			X	X	
Study drug administration		----- X -----							
Dispense study drug		X		X					
Collect study drug		X		X			X		
Telephone contact			X		X				
Adverse event collection		X	X	X	X		X	X	
Clinical chemistry		X		X			X	X	
BNP and NT-Pro BNP		X		X			X	X	
Hematology		X		X			X	X	
Urinalysis and microscopy		X		X			X	X	
Virus serology									
6-min walk test		X		X		X ^u	X ^u	X	
██████████		X		X		X	X	X	
████████████████████				X ⁿ			X ^o		
██████████							X		
WHO functional class ^p		X		X			X	X	
██████████		X		X			X		
██████████		X		X			X		
PK samples ^t		X ^s				X ^{s,t}	X ^t		

- a Total Screening period should not exceed 90 days.
- b Screen B is only required for patients if the Day 1 visit is more than 28 days after the Screen A visit.
- c Day 1 is the day of administration of the first dose. **On Day 1, all procedures should be performed before study drug administration.**
- d Screening eligibility procedures do not need to be repeated on Day 1; however, a review of any changes in eligibility criteria should be evaluated prior to Day 1 procedures, and a urine pregnancy test should be performed for WOCBP.
- e If an echocardiogram has not been performed within 90 days of Day 1, echocardiogram must be performed during Screening to confirm left ventricular ejection fraction $\geq 40\%$.
- f [REDACTED]
- g Pulmonary function tests within 90 days prior to Day 1 may be used to determine eligibility.
- h [REDACTED]
- i Right heart catheterization within 36 months prior to Day 1 may be used to determine eligibility.
- j Patients who have not had a V/Q scan, spiral/helical/electron beam computed tomography (CT), or pulmonary angiogram prior to Screening should have this assessment performed to determine eligibility. If V/Q scan is abnormal at Screening (*i.e.*, results other than normal or low probability), then a confirmatory CT or selective pulmonary angiography must also be performed at Screening to exclude chronic thromboembolic pulmonary hypertension (CTEPH).

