5.1. Definition of baseline

This section describes which measurements taken prior to first dose of study drug will be used to calculate baseline for each study parameter. No measurement collected after first dose will be used in the calculation of baseline. The collection date and time of the sample will be compared to the date and time of first dose. Should a patient never receive study drug, only measurements collected prior to randomization will be used in the calculation of baseline values.

In general, the baseline value for any laboratory or non-laboratory parameter will be calculated as the mean of data sampled up until and including Day 1, but not occurring after first dose of study drug, except in the following circumstances:

- Whenever specific visit results (i.e., Screening A, B, or Day 1) are indicated, the results will be used regardless of whether the measurements were collected within the protocol-specified window of time ([Appendix D](#)), as long as they precede first dose.
- For eligibility purposes, only two 6MWT observations (Screening B and Day 1 preferred to Screening A and Day 1) will be used to determine eligibility (must be within 15% of each other and at least 150 m). Patients not meeting the eligibility criteria are listed.
- As the covariate in the primary efficacy analysis, the screening 6MWT will be either the average of Screening A 6MWT and Screening B 6MWT or the single Screening A 6MWT result if Screening B did not occur.
- For the outcome in primary analysis, the Day 1 6MWT will be subtracted from the 6MWT observation at each followup time to give the change score.
- For discrete efficacy outcomes, [REDACTED], the latest assessment will be used for analysis purposes.
- If a scheduled measurement prior to first dose is repeated, baseline calculations will use only one result per scheduled measurement (i.e., either the original or repeated). The original value will be used, unless it is missing. The repeated value will only be used if the original value is missing, otherwise the repeated value will be ignored. The CSR will include listings of all repeated measurements collected prior to first dose, indicating whether they were included in the calculation of baseline.

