11. STATISTICAL METHODS

11.1. Primary efficacy outcome

11.1.1. Primary analysis

This section describes the methods planned for the primary analysis, which is based on the primary efficacy outcome, the change from baseline in 6MWT. The analysis will compare the mean change in the bardoxolone methyl group relative to placebo at Week 24. A mixed model will be fit with this outcome using the following PROC MIXED code in SAS, where ID is the patient identifier, SCR_6MWT and DELT_6MWT are the screening values for the 6MWT and change from baseline, respectively, in the primary outcome at each visit (VOBS) by treatment group (GRP), and N_PAH_MEDS is the fixed number of background PAH therapies for a patient. Below is example code used to estimate the treatment effect:

```
proc mixed data = &DAT. method=reml alpha=0.05 covtest;
  class ID GRP (ref="plc") VOBS (ref=LAST)
    N_PAH_MEDS;
  model DELT_6MWT = SCR_6MWT
                    N_PAH_MEDS
                    GRP
                    VOBS
                    GRP * VOBS
                    VOBS * SCR_6MWT Hb / s ddfm=kr;
  repeated VOBS / subject = ID type = UN r;
  lsmeans VOBS * GRP / diff om cl e;
run;
```

The model will have the following characteristics:

- The response variable will be the vector of observed change in the primary efficacy outcome from baseline at each study visit where the 6MWT is measured (Week 4, Week 8, Week 16, and Week 24). The outcome will consist of the following four repeated measures: Week 4 6MWT – baseline 6MWT, Week 8 6MWT – baseline 6MWT, Week 16 6MWT – baseline 6MWT, and Week 24 6MWT (averaged over both measurements made at Week 24) – baseline 6MWT. [REDACTED] 6MWT values collected after the date of clinical worsening will be treated as missing for analysis of 6MWT.
- Repeated post-baseline measurements from each patient will be identified by patient identifier (ID).
- Within-patient correlations will be modeled using an unstructured covariance structure. In the unlikely situation that this model does not converge (i.e., the study has too few observations for the number of parameters estimated), the model will use the heterogeneous Toeplitz structure, which assumes the correlation between two repeated measurements depends solely on their lag in visit number, and that the variance of the outcome may differ over time. If the model still does not converge

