with the heterogeneous Toeplitz structure, the model will use a homogeneous Toeplitz structure. Finally, if the model using the homogeneous Toeplitz structure does not converge, the model will use a compound symmetry structure which assumes equal correlation for a patient's measurements, regardless of how far apart in time they were taken.

- The models will include the following covariates:
 - Time defined as a categorical variable (i.e., no restriction is imposed on the trajectory of the mean outcome over time) (VOBS)
 - Treatment group (GRP)
 - N_PAH_MEDS (stratification variable for number of background PAH therapies)
 - Screening 6MWT (SCR_6MWT)
 - Screening 6MWT by time interaction (VOBS * SCR_6MWT)
 - Day 1 hemoglobin (Hb)
 - Time by treatment group interaction (GRP * VOBS)

The MMRM, as defined above, uses the screening value of the 6MWT as a covariate and the baseline value of the 6MWT for the computation of the outcome (the change from baseline). This allows adjustment for the “baseline” value between groups while providing the ability to provide valid estimates of the placebo-adjusted treatment effect.

In the event the MMRM model with an unstructured covariance structure does not converge, the following covariance structures are substituted, in the order listed. Each subsequent covariance structure is used only if each previous covariance structure is used and no previous model converged.

1. Heterogeneous Toeplitz covariance structure (assuming different variances at each time point and that measurements taken closer together in time are more highly correlated than those taken farther apart).
2. Toeplitz covariance structure (assuming measurements taken closer together in time are more highly correlated than those taken farther apart).
3. First order auto-regressive [AR(1)] covariance structure (assuming measurements taken closer together in time are more highly correlated than those taken farther apart, but the correlation is more constrained than the Toeplitz structure).
4. Compound symmetry covariance structure (assuming equal correlation for measurements from a patient, regardless of how far apart in time they were taken). A compound symmetry covariance structure was assumed in the sample size calculation.

Results of MMRM are summarized in tables and line plots. Additionally, line plots of 6MWT change from baseline, labeled by treatment group up to and including Week 24 are generated

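### The primary model subtracts the Day 1 walk but adjusts only for the screening walk; also adjusting for Day 1 would give a small, nearly free gain in precision

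*SAP*

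**What the plan says.** SAP 5.1 gives the two pre-dose walks different jobs. For the outcome, "the Day 1 6MWT will be subtracted from the 6MWT observation at each followup time to give the change score". For the covariate, "the screening 6MWT will be either the average of Screening A 6MWT and Screening B 6MWT or the single Screening A 6MWT result", the single value being used when there was no Screening B.

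SAP 11.1.1 carries this into the code. The only walk terms in the MODEL statement are SCR_6MWT and its visit interaction, and the statement closes with "VOBS * SCR_6MWT Hb / s ddfm=kr". The covariate list in that section agrees: visit, treatment, treatment by visit, number of background PAH therapies, screening 6MWT, screening 6MWT by visit, and Day 1 hemoglobin. The Day 1 walk is absent.

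The split is deliberate: SAP 11.1.1 says that the model "uses the screening value of the 6MWT as a covariate and the baseline value of the 6MWT for the computation of the outcome". The stated reason is that it adjusts for the baseline "value between groups while providing the ability to provide valid estimates of the placebo-adjusted treatment effect". Protocol 12.3.1 leaves the choice of covariates to the SAP.

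**The concern.** The baseline that enters the outcome is Day 1; the baseline that is adjusted for is screening. Where a patient walked unusually far or short on Day 1 by chance, that error goes with opposite sign into every change score, and the screening walk can remove only part of it. For the same reason, a chance difference between arms in Day 1 walk, given screening, is only partly corrected.

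The screening walk may also be some weeks old. Protocol Table 3 allows up to 90 days of screening, and "Screen B is only required for patients if the Day 1 visit is more than 28 days after the Screen A visit". Where Screen B is done, the covariate averages it with the older Screen A.

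At stake is precision, not validity: the standard error of the primary treatment effect may be somewhat larger than the collected data require.

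**Working it through.** **No plan figure to reproduce.** Effect size, SD, correlation and dropout are redacted in SAP 2.4 and Appendix A. What the documents give is about 130 patients, 65 per arm (SAP Appendix B.2), alpha 0.05 in the code, Week 24 as the mean of two walks (SAP 11.1.1), and eligibility requiring the two pre-dose walks to agree within 15% and to reach 150 m (SAP 5.1). The 8% test CV is the COPD figure in the walk-test guideline in Protocol Appendix 1. The other inputs are assumptions.

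**Formula.** Let S be the screening walk, D the Day 1 walk and W the Week 24 mean. The plan leaves Var(W - D | S). With Day 1 added it becomes Var(W | S, D). The difference is (1 - b)² × Var(D | S), where b is the slope of W on D given S. In large samples this cannot be negative, so the direction does not depend on the redacted inputs.

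**Worked case without the 15% rule.** Take between-patient SD 80 m, test SD 5% × 380 = 19 m, true-change SD 40 m, and no gap.
- Var(W - D) = 1600 + 361/2 + 361 = 2141.5. Its covariance with S is zero, so screening removes nothing.
- Var(D | S) = 6761 - 6400²/6761 = 702.7.
- b = (6400 - 6400²/6761)/702.7 = 0.486.
- Reduction = 0.514² × 702.7 ≈ 185, and 185/2141.5 = 8.7%.

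**With the eligibility rules** (simulation, 1,000,000 patients per scenario). The same case gives 7.0%, because the 15% rule caps the disagreement between S and D. Drift between screening and Day 1 was given variance (true-change SD²/168) × gap in days. Reduction in Week 24 residual variance at between-patient SD 80 m:

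| Test CV, true-change SD | No gap | 14 days | 28 days |
|---|---|---|---|
| 5%, 40 m | 7.0% | 5.4% | 4.5% |
| 5%, 60 m | 3.5% | 2.2% | 1.4% |
| 8%, 40 m | 8.8% | 7.7% | 6.9% |
| 8%, 60 m | 5.2% | 3.9% | 3.1% |

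Repeating the simulation with a new seed agrees to within 0.3 points. Between-patient SD 100 m changes the entries by at most 0.2 points. Screening alone removes 0-0.3% of the change-score variance in these cases.

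**In trial terms**, for the 7.0% case (residual variance 2103 falling to 1955):
- The half-width is 1.96 × √(2 × 2103/65) = 15.8 m, falling to 15.2 m.
- An assumed 80% power has normal deviate (1.960 + 0.842)/√0.930 - 1.960 = 0.945, which is 82.8%.
- Over the whole table the half-width falls by 0.2-0.8 m from 16-24 m, and power becomes 80.6-83.5%.
- Chance Day 1 imbalance given screening moves the estimate by SE × √(reduction) = 8.04 × √0.070 = 2.1 m (1 SD); the range is 1.4-2.7 m. This restates the same loss in metres and is not a second one.

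**Sensitivity.**
- Change falls with walk level (slope -0.2): gain 3.4-12.7%. Change rises with level (+0.2): gain 0.3-5.8%. With either slope the screening walk itself removes about 3-14%.
- True-change SD 20 m, so that test error dominates: 14-16%.
- Screening as the average of walks 60 and 14 days before Day 1: 2.0-10.9%.
- Other assumptions (mean 400 m, between-patient SD 100 m, noise SD 15-32 m), simulated at 130 patients with the eligibility rules: variance ratio 0.82 to about 1.00.
- Upper bound, if all raw walks including Week 24 were exchangeable: variance ratio 0.58-0.66.

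**Full MMRM check.** Week 24 data will be incomplete, partly by rule: "6MWT values collected after the date of clinical worsening will be treated as missing for analysis of 6MWT". The check used four visits, unstructured REML, three strata, Hb, 130 patients, 88% observed at Week 24 (missing at random), between-patient SD 90 m and 5,000 trials per scenario. Model variance of the Week 24 effect fell by 2.5-7.4% with no gap and 0.5-5.7% with 28 days, with the extra parameters paid for. Power rose from 79.3-82.8% to 80.2-85.3%. Type I error was 0.047-0.056 as planned and 0.046-0.056 with Day 1. Bias was at most 0.23 m in both.

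**The case against.** The strongest reply is that nothing is broken. The choice is deliberate, prespecified and valid, and preferring another valid covariate set is a matter of taste. That stands as a description of the plan. But the SAP's reason for splitting the walks does not argue against using Day 1 as well, and the model already takes one Day 1 covariate, hemoglobin. Redacted text may hold further reasons, and this cannot be excluded.

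Second, blinded sample size re-calculation (Protocol 7.1.1, SAP Appendix B) can protect power by adding patients, up to about 200. That is right, so power is not left short for this reason alone. It does not restore precision per patient.

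Third, the gain is not guaranteed to be positive at 130 patients. If change rises with walk level (+0.2) and the gap is 28 days, the low-end gain of 0.3% is less than the cost of one parameter, about 1/130 = 0.8%. This is one unfavourable corner of the range.

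Fourth, the two walks are strongly correlated. That makes their separate coefficients imprecise, but not the randomized treatment contrast.

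Fifth, the size depends on assumed inputs. This stands. Other inputs can make the gain larger as well as smaller, so even the word small is conditional.

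**Conclusion.** The point holds as an improvement to consider, not as a fault. The planned analysis is valid. Under the base-case assumptions it gives up 1.4-8.8% of Week 24 residual variance, worth 0.2-0.8 m of half-width and 0.6-3.5 points on an assumed 80% power. The four-visit model with missing data gives 0.5-7.4% less variance. The gain is near zero, or slightly negative after the parameter cost, if change rises with walk level and screening is four weeks old. It is 14-16% if test error dominates. By itself it is unlikely to change the trial's conclusion. It is still worth making because it concerns the primary test, in a trial of about 130 patients, and uses data already in hand.

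**What to change.** Before unblinding, add Day 1 6MWT and Day 1 6MWT by visit to the MODEL statement, beside SCR_6MWT and VOBS*SCR_6MWT and not in their place. Leave the outcome, strata, hemoglobin and covariance structure unchanged. With the visit interaction in the model, analysing change or the raw walk gives the same treatment effect.

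No patient should be lost. The change score already needs the Day 1 walk, eligibility uses it (Protocol 9.10.26), and Protocol Table 3 places it before dosing: "On Day 1, all procedures should be performed before study drug administration".

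The cost is one line of code, one SAP sentence and about one degree of freedom at Week 24 (four parameters in all), plus the approval that any revision of a primary model needs. No new data are required and the estimand is unchanged. If Day 1 is left out on purpose, one sentence added to the rationale in SAP 11.1.1 is enough.

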11.2. Secondary efficacy outcome

The secondary efficacy outcome, the time to clinical improvement, will be analyzed using methods for a censored time-to-event outcome. All analyses will be stratified using number of background PAH medications at baseline to define the strata.

Summary tables will present median time to first clinical improvement and associated 95% CIs for each treatment group as well as hazard ratios and 95% CIs for each comparison of bardoxolone methyl to placebo. Median duration with appropriate 95% CIs, as well as the proportion of patients remaining event-free at times of interest, will be estimated using Kaplan-Meier methods with the product limit estimator computed using PROC LIFETEST in SAS.

PROC PHREG in SAS will be used to estimate hazard ratios, mean and standard error time -to-event, and their 95% CIs by Cox regression models.

[REDACTED]

In the event that the number of events across strata is too small, the strata consisting of zero background PAH medications and one background PAH medication will be collapsed.

[REDACTED]

[REDACTED]

Treatment group comparisons will use the Type 3 Chi-square test and unadjusted two-sided p-value associated with the treatment group variable in the Cox proportional hazards model. Time-to-event analyses will use Breslow's method of handling ties in event times [1], which is the default method used in PROC PHREG. The TEST statement in PROC LIFETEST will be used to include the strata and the STRATA statement will be used in PROC PHREG.

Kaplan-Meier plots will supplement these presentations. The number of patients within each treatment group at risk of an event at regular time points will appear at the bottom of these figures.

The secondary outcome is important in understanding the effectiveness of bardoxolone methyl and its ability to improve function.

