5. GENERAL CONVENTIONS

The protocol-specified time windows for a visit ([Appendix D](#)) and time of a measurement (Section [5.4](#)) determine the visit assignment for each observation.

Continuous data will be summarized using descriptive statistics: number of observations (n), mean, median, standard deviation (SD), minimum, and maximum. Confidence intervals (CIs) will be presented as appropriate. The same number of decimal places as in the observed value will be presented when reporting minimum and maximum; 1 more decimal place than in the observed value will be presented when reporting mean and median; and 2 more decimal places than in the observed value will be presented when reporting SD. When values are averaged in the analysis data (e.g., in the calculation of baseline), the same number of decimal places as in the observed value will be presented.

Frequencies and percentages will summarize categorical data. Presentations of categorical data will generally suppress percentages for items where the count is zero in order to draw attention to nonzero counts.

Confidence intervals will generally be constructed at the 95% level. For binomial variables, exact methods will be employed unless otherwise specified.

Categorical/qualitative data will be presented using frequency counts and percentages. All percentages will be rounded to 1 decimal place, unless otherwise specified. Percentages equal to 100 will be presented as 100% and no percentages will be presented for zero frequencies.

Summary presentations will classify patients by their randomized treatment group for analyses on the ITT population, and actual treatment received for analyses on the safety population, unless otherwise specified. References to treatment group from this point forward in the SAP text indicate randomized treatment group, unless stated otherwise.

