7.3. Demographic and baseline characteristics

Summaries of demographic and other baseline characteristics will be presented by treatment group for all analysis populations (Section 3). The two treatment groups will be assessed descriptively for comparability of demographic and baseline characteristics for the ITT study population. Demographics and baseline characteristics will be summarized by subgroups.

Demographics and other baseline characteristics include the following:

- age (years) at the date of informed consent, sex, ethnicity, race
- height, weight, body mass index (BMI)
- baseline disease characteristics (e.g., WHO functional class, baseline 6MWT, years since PAH diagnosis)
- connective tissue disease (CTD) etiology (scleroderma, lupus, mixed, and other)
- pulmonary function testing results
- PAH and CTD medications
- geographic region
- baseline eGFR
- baseline eGFR category
 - ≥ 90 (ml/min/1.73m²)
 - 60 to < 90 (ml/min/1.73m²)
 - 45 to < 60 (ml/min/1.73m²)
 - 30 to < 45 (ml/min/1.73m²)
 - 15 to < 30 (ml/min/1.73m²)
 - < 15 (ml/min/1.73m²)
- other variables of interest

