10.2. Secondary efficacy outcome

The secondary efficacy outcome is the time-to-first persistent clinical improvement event. To declare that clinical improvement has occurred, at least one of the following four criteria must be met:

1. Improvement by at least one WHO functional class coupled with no more than a 15% decrease from baseline in 6MWT.
2. Increase from baseline in 6MWT by at least 10% and stability or improvement in the WHO functional class.
3. Decrease from baseline in creatine kinase (a surrogate biomarker for muscle injury and inflammation) by at least 10% and no worsening in WHO functional class and no more than a 15% decrease from baseline in 6MWT.
4. Improvement in estimated glomerular filtration rate (eGFR) $\geq 10\%$ of baseline.

The persistence of the change in WHO functional class, 6MWT, eGFR, or creatine kinase must be confirmed by a subsequent assessment that also meets the defined criteria. The confirmatory assessment must occur at least 14 days after the initial assessment, or at the next scheduled assessment. If persistent improvement is confirmed, the date of the event will be considered the initial assessment of improved WHO functional class, 6MWT, eGFR, or creatine kinase.

If confirmatory observation of initial improvement is not available for any reason, such as end of study or death, it may or may not be considered an event as defined by the timing of improvement as it relates to other study events. Below is a list of possible reasons for failure to obtain a confirmatory observation along with the adjustment to the definition of improvement.

These reasons are as follows:

1. Last visit: If the improvement is observed at the last scheduled assessment, the requirement for an additional assessment after 14 days is waived, and the patient is classified as satisfying the criteria for improvement. In the absence of study end date, Study Drug Termination (SDT) is used.
2. Death: If the patient's death occurs before the confirmatory observation, then the patient is classified as not satisfying the criteria for improvement.
3. Study termination: If the patient terminates the study for reasons of "lost to follow-up" or "withdrawal of consent", then the patient is classified as not satisfying the criteria for improvement.
4. Patient starts new PAH drug: If a patient decides to stop study drug and switch to a new PAH drug, then the patient is classified as not satisfying the criteria for improvement.

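### Secondary Cox model: the visible text shows PAH-count strata and no other covariate; adding the baseline values behind the four criteria is an optional, nil-to-modest efficiency gain

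*SAP*

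**What the plan says.** SAP 11.2 sets out the analysis of the secondary outcome: "All analyses will be stratified using number of background PAH medications at baseline to define the strata". On implementation it adds: "The TEST statement in PROC LIFETEST will be used to include the strata and the STRATA statement will be used in PROC PHREG". The test is described as follows: "Treatment group comparisons will use the Type 3 Chi-square test and unadjusted two-sided p-value associated with the treatment group variable". On ties: "Time-to-event analyses will use Breslow's method of handling ties in event times". Three blocks of SAP 11.2 are redacted, one of them directly after the sentence that introduces the Cox models.

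SAP 10.2 defines four ways to have an event, each relative to the patient's own starting point. The first reads: "Improvement by at least one WHO functional class coupled with no more than a 15% decrease from baseline in 6MWT". The others are a 10% gain in 6MWT, a 10% fall in creatine kinase (CK) and a 10% gain in eGFR. Three of the four also use class or 6MWT as a guard condition.

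The baseline values are on file. Protocol Table 3 schedules functional class, 6MWT and clinical chemistry before the first dose. The chemistry panel (Protocol 9.10.21) contains CK and creatinine. SAP 7.3 already summarises "baseline disease characteristics (e.g., WHO functional class, baseline 6MWT, years since PAH diagnosis" and, separately, baseline eGFR.

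The primary model (SAP 11.1.1) does adjust for baseline information, namely screening 6MWT and Day 1 hemoglobin.

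**The concern.** When an event is a change from one's own baseline, the baseline can predict the event. Entry is limited to class II and III, so a one-class improvement is a different step for the two groups. A 10% walk gain is 15 m from the 150 m entry floor (0.10 × 150) but 45 m from 450 m (0.10 × 450), the cut used for subgroups in SAP 15.3. A CK value that is high by chance, or an eGFR that is low by chance, can also drift back across a 10% threshold.

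Leaving a prognostic covariate out of a Cox model pulls the treatment hazard ratio towards 1 and costs power, more so when events are common. The SAP calls this outcome important for understanding the drug's effectiveness. No power for it is visible, and the readable text gives no reason why the primary model adjusts for baseline and this one does not.

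**Working it through.** **No figure to reproduce.** The readable text gives no power, hazard ratio or event count for this endpoint.

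**Inputs from the documents.** N = 130, possibly 200; 1:1 allocation; three PAH-count strata; Breslow ties; in-person visits at Weeks 1, 2, 4, 6, 8, 16 and 24. A two-sided alpha of 0.05 is assumed from the convention "Confidence intervals will generally be constructed at the 95% level".

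**Assumed inputs, not in the documents.** Conditional hazard ratio (HR) 1.75; placebo event probability about 0.6 by Week 24; stratum mix 10/40/50%; no dropout; four independent covariates, each with log-HR b per SD.

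**Benchmark (Schoenfeld).** Power = Φ(√D/2 × ln HR − 1.96), with D events.
- N = 130, 50% events: D = 65, so 4.031 × 0.5596 − 1.96 = 0.296 and power is 61.6%. With 70% events it is 76.1%.
- N = 200: 79.9% and 91.2%.

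**Simulation of the stratified Cox model.** 600 runs per cell; Monte Carlo SE about √(0.6 × 0.4/600) = 2 points. The combined baseline score has SD √(4b²) = 2b.

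| b | Score SD | N=130: strata only → adjusted | Change | N=200: strata only → adjusted | Change |
|---|---|---|---|---|---|
| 0 | 0 | 63.8 → 64.8% | +1.0 | 83.7 → 84.3% | +0.6 |
| 0.1 | 0.2 | 62.3 → 61.3% | −1.0 | 83.0 → 82.7% | −0.3 |
| 0.2 | 0.4 | 59.3 → 63.3% | +4.0 | 77.8 → 82.7% | +4.9 |
| 0.3 | 0.6 | 51.3 → 61.2% | +9.9 | 71.7 → 84.3% | +12.6 |
| 0.5 | 1.0 | 38.7 → 59.7% | +21.0 | 58.0 → 79.0% | +21.0 |

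**Where a gain comes from.** At N = 130 and b = 0.3, the mean HR moves from 1.56 to 1.65 while the SE of the log HR rises from 0.222 to 0.229 (+3%). The ratio of log HR to SE goes from 0.445/0.222 = 2.00 to 0.501/0.229 = 2.19. At b = 0.5, the HR moves from 1.45 to 1.66 and the SE from 0.224 to 0.234 (+4%). The gain is therefore a shift in the estimated hazard ratio and not better precision.

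**Type I error.** In 1,000 null runs per setting at N = 130 (b = 0, 0.3 and 0.5), rejection was 1.9 to 3.5% with strata only and 2.4 to 3.4% adjusted.

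**Which row is realistic?** Each baseline drives mainly its own component of an any-of-four composite, so its pull on the composite is diluted. Two direct simulations of the composite addressed this.
- The first used confirmed events, the walk coefficient of variation of about 8% given in the walk-test guideline (Protocol Appendix 1), and assumed CK and eGFR noise, class-improvement rates and treatment effects, with 250 to 500 runs per setting. The fitted score SD was about 0.2 to 0.3, power changed by about −2 to +4 points, and null rejection was 3% in both models.
- The second, with strata and Breslow ties, gave a score SD of about 0.2 to 0.5 and changes of about −2 to +5 points.

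Both fall around the 0.2 and 0.4 rows of the table. The negative values are within simulation error.

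**The case against.** The strongest reply is that nothing is broken. The Cox model is stratified on the randomisation factor, its test is valid, and no visible power target is missed. That stands, and it is why the point is optional.

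Three stronger readings are tempting, and the documents do not support them.

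- **That the model adjusts only for PAH count.** A redacted block sits exactly where covariates would be listed, and blacked-out text is not missing from the plan. The word unadjusted in the description of the p-value does not settle it, since it can equally refer to multiplicity.
- **That adjustment is free.** The hazard ratio becomes conditional on the covariates and no longer corresponds to the Kaplan-Meier curves and medians shown beside it. The SE rises slightly, and functional forms and a missing-value rule are needed.
- **That the gain is large.** Gains of 10 points or more need a score SD of about 0.6 or higher, and nothing in the documents supports that strength.

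The regression-to-the-mean argument is also partly met already. SAP 5.1 generally averages pre-dose values, SAP 10.2 requires confirmation in most cases, and the two eligibility walks must agree within 15%. These steps reduce baseline noise but do not remove it. That class III improves more readily than class II is plausible but has no source in the documents.

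Four extra parameters could look heavy, given that SAP 11.2 foresees collapsing strata when events are few. Under the assumed event rate the load is acceptable: 0.67 × 130 ≈ 87 events over five parameters is about 17 events each. With far fewer events this objection would gain weight.

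**Conclusion.** The point holds as an optional efficiency improvement. In the visible text the secondary Cox model carries PAH-count strata and no other covariate, while every criterion is anchored to a baseline value already collected. Adding those values is valid and would be expected to raise power by about 0 to 5 points, more only if the baselines prove strongly prognostic. The planned test needs no correction.

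The size rests on assumed hazard ratios, event rates, measurement noise and prognostic strength, none of which the documents supply for this endpoint. The finding that adjustment does not inflate type I error depends less on them: null rejection stayed below 5% at every prognostic strength tried.

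**What to change.** If the redacted text of SAP 11.2 does not already do so, add the following before unblinding:

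1. Keep the PAH-count strata in PROC PHREG. Add WHO class (II/III), 6MWT, log CK and eGFR at baseline as covariates in the model used for the treatment test and hazard ratio.
2. Name the baseline value for each covariate under SAP 5.1. That section has a general averaging rule, a latest-value rule for discrete efficacy outcomes, and separate screening and Day 1 walk values for the primary model. The natural choice is the value against which the criterion itself is judged.
3. State a missing-baseline rule, so that no randomised patient drops out of the model.
4. State that the hazard ratio is conditional on these covariates. Report the strata-only hazard ratio as supportive, beside the Kaplan-Meier summaries.

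No new data are needed. The cost is a short paragraph in the SAP, one more model run, a conditional estimand to explain, and a slightly larger standard error. If the sponsor prefers the strata-only model, a sentence giving the reason would be enough.
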